## 6.5. Study Drug Compliance

For participants in the safety population, overall compliance (%) for parsaclisib will be calculated for all participants as

$$\text{compliance (\%)} = 100 \times [\text{total dose actually taken}] / [\text{total prescribed dose}].$$

The total prescribed dose is defined as the sum of the doses prescribed by the investigator accounting for dose modifications.

The total actual dose taken will be calculated based on information entered on the Drug Accountability CRF. If there are dispensed drugs that have not been returned yet, the actual dose taken starting from the dispense date of the unreturned drugs will be imputed by the dose taken as reported on the dosing CRF.

## 6.6. Prior and Concomitant Medication

Prior medications and concomitant medications will be coded using the WHO Drug Dictionary. Number and percentage of participants in the FAS for each prior and concomitant medication will be summarized by WHO drug class and WHO drug PT.

## 7. EFFICACY

[Appendix A](#) provides a list of planned tables, figures, and listings. Sample data displays are included in a separate document.

### 7.1. Efficacy Hypotheses

Not applicable.

### 7.2. Response Assessment

An objective assessment of disease status is required at baseline (screening) using the CT-based response criteria of the Lugano Classification ([Cheson et al 2014](#)). Disease status will be subsequently assessed by CT/MRI every 8 weeks through Week 24, then every 12 weeks through Week 96, and then every 24 weeks thereafter until disease progression.

Bone marrow examination is required as a baseline assessment at screening except for reasons provided in Section 8.2.2 of the Protocol. If disease is present in bone marrow at baseline, a bone marrow examination will be required to confirm CR or may be performed as clinically indicated. If the bone marrow does not have lymphoma involvement at baseline, a repeat marrow examination is not required to confirm indication of CR on imaging. All bone marrow examination should include a unilateral aspiration and biopsy, when feasible.

Sites will use the CT-based response criteria of the Lugano Classification ([Cheson et al 2014](#)) to assess response to treatment locally. At each postbaseline disease assessment, response will be collected in the eCRF as CR, PR, SD, PD, or NE.

All imaging will be submitted to the IRC. Imaging data and applicable clinical data will be reviewed and response will be assessed using the CT-based response criteria of the Lugano Classification ([Cheson et al 2014](#)) by independent reviewers as described in the Independent Review Charter. An overall timepoint response at each postbaseline disease assessment, the best overall response, the date of initial response (if applicable), and the date of progression along with the reason(s) of disease progression (if applicable) for each participant, considering radiographic data and clinical data, will be provided by the clinical reviewer. These data will be used in the analyses of related efficacy endpoints.

### 7.3. Analysis of the Primary Efficacy Parameter

The primary efficacy analysis will be conducted when the last patient in the FAS has been followed for 12 months from the first dose of treatment.

#### 7.3.1. Best Overall Response and Overall Response Rate

For responses determined by the IRC, the best overall response for each participant will be provided by the clinical reviewer. A participant is considered an objective responder if they have a best overall response of CR or PR.

The ORR is the proportion of objective responders. Participants who do not have sufficient baseline or on-study response assessment information to be adequately assessed for response status will be included in the denominators in the calculation of ORR.

Best overall response as determined by the IRC will be descriptively summarized. The ORR as determined by the IRC will be estimated with 95% CIs. Confidence intervals will be calculated based on the exact method for binomial distributions.

When applicable, sensitivity analysis of ORR as determined by the IRC may be provided excluding participants who do not have evaluable radiological images at baseline per the IRC.

### **7.3.2. Subgroup Analyses for Objective Response Rate**

Subgroups will be formed based on the following participant characteristics and baseline variables for those participants whose data are available:

- Age: < 65 years,  $\geq$  65 years
- Gender: male, female
- Current FL grade: 1, 2, 3a
- Current Ann Arbor Staging: I-II, III-IV
- Current FLIPI risk category: low (0 - 1), intermediate (2), high ( $\geq$  3)
- Number of prior systemic therapy regimens: 2,  $\geq$  3
- Bone marrow involvement at baseline: yes, no, unknown
- ECOG performance status:  $\leq$  1 versus 2
- Bulky disease at baseline: longest diameter  $\geq$  10 cm vs < 10 cm at baseline by IRC
- Relapsed/refractory status to the most recent prior therapy: relapsed, refractory, unknown
- Prior history of ASCT: yes, no

Subgroups may be further divided, combined, or eliminated based on emerging data. The ORR as determined by IRC and its 95% exact binomial CIs will be provided for participants for each subgroup. A forest plot will be created to summarize the variability in ORR as determined by the IRC for participants across subgroups.

## **7.4. Analysis of the Secondary Efficacy Parameters**

### **7.4.1. Complete Response Rate**

Complete response rate is the percentage of participants with a best overall response of CR as defined by revised response criteria for lymphomas ([Cheson et al 2014](#)). For responses determined by the IRC, the best overall response for each participant will be provided by the clinical reviewer. Participants who do not have sufficient baseline or on-study response assessment information to be adequately assessed for response status will be included in the denominators in the calculation of CRR.

The CRR as determined by the IRC will be estimated with 95% CIs. Confidence intervals will be calculated based on the exact method for binomial distributions.

#### **7.4.2. Duration of Response**

Duration of response is defined as the time from first documented evidence of CR or PR until disease progression or death due to any cause among participants who achieve an objective response (ie, CR or PR), as determined by revised response criteria for lymphomas (Cheson et al 2014). For responses assessed by the IRC, the date of initial response and date of disease progression will be provided by the clinical reviewer for participants who have achieved best response of CR or PR. Censoring of DOR will follow the same algorithm as the censoring of PFS (see Section 7.4.3).

The total number of responders per the IRC, the number of participants whose disease progressed per the IRC or who died, and the number of participants censored will be summarized. The Kaplan-Meier estimate of median DOR as determined by the IRC will be presented with its 95% CI, with the CIs calculated using the generalization of Brookmeyer and Crowley's method (1982) with log-log transformation (Klein and Moeschberger 1997).

#### **7.4.3. Progression-Free Survival**

Progression-free survival is defined as the time from the date of the first dose of the study drug to the first documented disease progression as determined by revised response criteria for lymphomas (Cheson et al 2014), or death due to any cause, whichever occurs first. For responses assessed by IRC, date of disease progression will be provided by the Clinical Reviewer. Censoring for PFS will follow the algorithm outlined in Table 2, which is based on FDA Guidance for Industry: Clinical Trial Endpoints for the Approval of Non-Small Cell Lung Cancer Drugs and Biologics (2015) and Guidance for Industry: Clinical Trial Endpoints for the Approval of Cancer Drugs and Biologics (2018).

The number of participants whose disease progressed per the IRC or who died, and the number of participants censored will be summarized. The Kaplan-Meier estimate of median PFS as determined by the IRC will be presented with its 95% CIs, with the CIs calculated using the generalization of Brookmeyer and Crowley's method (1982) with log-log transformation (Klein and Moeschberger 1997). Progression-free survival rates at 6, 12, 18, and 24 months will also be provided with 95% CIs calculated using Greenwood's formula to estimate the standard error.

**Table 2: Evaluation and Censoring of Progression-Free Survival**

Situation	Outcome	Date of Progression or Censoring
No baseline tumor assessments	Censored	Day 1
No valid postbaseline response assessments	Censored	Day 1
Progression documented between scheduled response assessments	Progressed	Date of first overall response of PD
No progression	Censored	Date of last valid radiologic assessment (not NE and not missing)
Study discontinuation for undocumented progression	Censored	Date of last valid radiologic assessment (not NE and not missing)
Study discontinuation for toxicity or other reason	Censored	Date of last valid radiologic assessment (not NE and not missing)
New anticancer treatment started	Censored	Date of last valid radiologic assessment (not NE and not missing) on/before starting a new anticancer treatment
Death before first progressive response assessment	Progressed	Date of death
Death between adequate response assessments	Progressed	Date of death
Death or progression after two or more missed assessments	Censored	Date of last valid radiologic assessment (not NE and not missing) before the missed assessments

NE = not evaluable.

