10.4.2. Analyses of Secondary Efficacy Endpoints

Complete response rate is the percentage of participants with a CR as defined by revised response criteria for lymphomas, as determined by an IRC. The CRR determined by the IRC and its 95% exact binomial CIs will be calculated.

Duration of response is defined as the time from first documented evidence of CR or PR until disease progression or death due to any cause among participants who achieve an overall response, as determined by IRC. For participants who have not progressed and are still alive at the time of the analysis, DOR will be censored on the day of last evaluable disease assessment. For participants who have discontinued study or have started other anti-lymphoma treatment, DOR will be censored on the day of last evaluable disease assessment documenting absence of PD before the discontinuation or the start of the new anti-lymphoma treatment. Kaplan-Meier estimation of median DOR per IRC and its 95% CIs will be provided.

Progression-free survival is defined as the time from the date of the first dose of study drug to the first documented disease progression as determined by IRC, or death due to any cause, whichever occurs first. For participants who have not progressed and are still alive at the time of the analysis, PFS will be censored on the day of last evaluable disease assessment. For participants who have discontinued study or have started other anti-lymphoma treatment, PFS will be censored on the day of last evaluable disease assessment documenting absence of PD before the discontinuation or the start of the new anti-lymphoma treatment. For participants who have no baseline or no postbaseline disease assessment, PFS will be censored with duration of 1 day. Kaplan-Meier estimation of median PFS per IRC and its 95% CIs will be provided.

Overall survival is defined as the time from the date of the first dose of study drug to death due to any cause. For participants who are still alive at the time of the analysis, OS will be censored on the date the participant is last known to be alive. The Kaplan-Meier estimation of median OS and its 95% CIs will be provided.

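### SAP Table 2 gives a death before any valid post-baseline scan two opposite PFS outcomes with no order of precedence, and the Protocol's 1-day rule, read literally, censors some of these deaths

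*SAP*

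**What the plan says.** SAP 7.4.3 defines PFS as the time from first dose to documented progression "or death due to any cause, whichever occurs first", and refers to Table 2 for censoring. Four rows of Table 2 matter here:

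- "No valid postbaseline response assessments": censored, Day 1.
- "No baseline tumor assessments": censored, Day 1.
- "Death before first progressive response assessment": event, date of death.
- "Death or progression after two or more missed assessments": censored at the last valid scan before the missed ones.

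No row order or hierarchy is given, and neither Day 1 row is limited to participants without an event. The same section plans to report "The number of participants whose disease progressed per the IRC or who died", alongside the number censored. SAP 7.5.2 applies the same methods to investigator-reported PFS.

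Protocol 10.4.2 also counts death from any cause. Its general rule is limited to survivors: "For participants who have not progressed and are still alive at the time of the analysis, PFS will be censored" at the last evaluable assessment. A later sentence in the same paragraph has no such limit: "For participants who have no baseline or no postbaseline disease assessment, PFS will be censored with duration of 1 day". SAP 11.1 lists no changes to Protocol-defined analyses, so the SAP does not claim to replace that sentence.

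**The concern.** The first post-baseline scan is due at Week 8 with a window of 1 week either side (Protocol Table 3), so it may fall as late as Week 9. A treated participant who dies before it has a PFS failure by definition, yet one row of Table 2 and the literal Protocol sentence remove that participant from the risk set at Day 1.

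Two programmers could code this case differently and both cite the plan. The direction of the error is known: Day 1 censoring discards failures, so the PFS curve, its median and the planned landmark rates come out too favourable. In an open-label single-arm study it is better not to settle the handling of early deaths after the data are seen.

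**Working it through.** **Step 1: classify the cases.** Rules are as worded in SAP Table 2 and Protocol 10.4.2. Each case is a death without prior progression and before any new anticancer therapy.

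| Case | SAP Day 1 row (no valid post-baseline scan) | SAP death row | Protocol 1-day sentence, literally |
|---|---|---|---|
| No post-baseline scan at all | meets it | meets it | censors |
| Only not-evaluable post-baseline scans | meets it | meets it | does not reach it (the sentence does not say valid) |
| At least one valid post-baseline scan, fewer than two missed | does not meet it | meets it | does not apply |
| Two or more missed scans, no valid post-baseline scan | meets it | meets it, and also the missed-assessments row | censors if there was no scan at all |

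The first two cases have contradictory outcomes in the SAP. In the fourth, the missed-assessments row has no post-baseline date at which to censor.

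**Step 2: size if the Day 1 rule is used.** The plan gives no PFS figure to reproduce: no assumed PFS level and no early-death rate. The only input from the documents is n = 40 (SAP 3.3). Assumed: k early deaths, and S_rest(t), the PFS of the other participants.

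- Deaths counted: S(t) = (1 - k/40) x S_rest(t).
- Deaths censored at Day 1: S(t) = S_rest(t).
- Ratio: 40/(40-k), which is 40/39 = 1.026 for k = 1 and 40/38 = 1.053 for k = 2.
- Absolute shift: S_rest(t) x k/40.
- Approximate 95% half-width: 1.96 x sqrt(S(1-S)/40), with S = S_rest and no censoring before t.

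| Timepoint | Assumed S_rest | Shift, k = 1 | Shift, k = 2 | Half-width |
|---|---|---|---|---|
| 12 months | 0.50 | 0.0125 | 0.025 | 0.155 |
| 12 months | 0.70 | 0.0175 | 0.035 | 0.142 |
| 6 months | 0.75 | 0.0188 | 0.0375 | 0.134 |
| 6 months | 0.85 | 0.0213 | 0.0425 | 0.111 |

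Table 2 censors for several other reasons, so the real intervals would be wider than these half-widths.

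**Step 3: median.** With an exponential curve in the others, counting the deaths multiplies the median by 1 - ln(1-k/40)/ln(0.5). This is 0.9635 for k = 1 and 0.9260 for k = 2, so the median is 3.7% or 7.4% shorter.

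**Step 4: how likely is k of at least 1?** Assume that each participant has a probability p of dying before the first scan. Then P(k >= 1) = 1 - (1-p)^40.

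- p = 0.005: 0.182, and P(k >= 2) = 0.017.
- p = 0.01: 0.331, and P(k >= 2) = 0.061.
- p = 0.02: 0.554, and P(k >= 2) = 0.190.

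**The case against.** The strongest reply is that the plan already points to the answer. Both documents define death from any cause as a PFS event, and the SAP plans a count of those who progressed or died. A reader might infer that Table 2 is applied from the top down, so that the Day 1 rows win. The documents do not support this. Nothing says that the rows run in order, and a strict top-down reading would let the no-progression row, which stands above both death rows, absorb every death without documented progression. Table 2 works only if the death rows override the general censoring rows. This stands, and it makes the death row the likely intent. It does not remove the overlap, and it does not touch the Protocol sentence, which contradicts the definition as worded.

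Three limits also stand:

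- A reader might infer that the Protocol rule censors every death that falls under the SAP's Day 1 row. It does not reach deaths after only not-evaluable scans.
- The row for a missing baseline assessment overlaps with the death row in wording, but it should be nearly empty. Inclusion criterion 6 requires measurable disease on CT or MRI, and Protocol section 5 allows no waivers.
- Few early deaths are expected, because inclusion criterion 9 requires a life expectancy of at least 12 weeks, beyond the latest date for the first scan.

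The size rests wholly on assumed values of k, p and PFS.

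**Conclusion.** The contradiction is in the current text of both documents and is worth correcting, at minor severity. The plan does not clearly intend to censor early deaths, and it would be wrong to read it that way. It leaves the case unresolved in the SAP and misworded in the Protocol.

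If the Day 1 rule were applied, PFS would be overstated by a factor of 1.026 for one early death among 40, or 1.053 for two. At 12 months, with PFS of 0.50 to 0.70 in the others, that is 1.3 to 1.8 points or 2.5 to 3.5 points, against a half-width of at least about 14 to 16 points. If the death row is used, there is no bias.

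A reader might also expect DOR to be affected, since SAP 7.4.2 borrows the PFS censoring rules. It is not, because a responder has a valid post-baseline scan by definition. ORR, the futility rule and OS do not use these rows. PFS is descriptive, with no formal test (Protocol 10.3, SAP 3.2).

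**What to change.** State in SAP 7.4.3 or under Table 2 that both Day 1 rows, and the Protocol 1-day rule, apply only to participants without a PFS event. A death without prior progression (per IRC or investigator, whichever is being analysed) and before new anticancer therapy is then an event on the date of death. Align the sentence in Protocol 10.4.2 at any later amendment.

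The sponsor should also state how a death after two or more missed assessments is handled when no valid post-baseline scan exists, because the retained row then has no post-baseline censoring date. Either choice can be defended. If such a death is made an event, it will be treated differently from the same death after a valid scan and two missed ones, and the SAP should say that this is intended.

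The cost is one or two SAP sentences and a small programming check. Reported PFS may be slightly less favourable.

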### 11.1. Changes to Protocol-Defined Analyses

Not applicable.

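### SAP Table 2 censors deaths and progressions after two or more missed assessments; Protocol 10.4.2 counts them as PFS and DOR events, and SAP 11.1 declares no change

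*SAP*

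**What the plan says.** SAP 7.4.3 sends PFS censoring to a table: "Censoring for PFS will follow the algorithm outlined in Table 2, which is based on FDA Guidance for Industry". The last row of Table 2 covers "Death or progression after two or more missed assessments". Its outcome is censored, and its date is "Date of last valid radiologic assessment (not NE and not missing) before the missed assessments". SAP 7.4.2 extends this to response duration: "Censoring of DOR will follow the same algorithm as the censoring of PFS". The investigator-reported PFS and DOR in SAP 7.5.2 are analysed as in 7.3 and 7.4, so they inherit the row too.

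Protocol 10.4.2 runs PFS from first dose "to the first documented disease progression as determined by IRC, or death due to any cause, whichever occurs first". It then gives three grounds for censoring:

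- For someone without progression and "still alive at the time of the analysis, PFS will be censored on the day of last evaluable disease assessment".
- Someone who left the study or began other anti-lymphoma treatment is censored at the last evaluable assessment before that.
- Someone with no baseline or no postbaseline assessment is censored at 1 day (PFS only).

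The first two also apply to DOR. None mentions missed assessments.

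SAP 11.1, headed "Changes to Protocol-Defined Analyses", records that there are none. SAP 11.2 reports only a change to the timing of the primary analysis.

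**The concern.** The same participant can be an event under the protocol and a censored observation under the SAP. Under the SAP rule, PFS and DOR no longer count every documented progression or death as the protocol defines them, and a reader of SAP 11.1 would not know.

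The participants concerned are foreseeable. Stopping treatment does not end study participation (Protocol 7.1). Imaging is meant to continue after treatment stops for reasons other than progression (Protocol 8.2.1). Survival contact may be by phone or email (Protocol Table 3), so a death can be known and dated although scans were missed. If scans are missed because a participant is declining, censoring at the last scan is informative.

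Nothing planned would reveal the effect. The table and figure lists in SAP Appendix A contain no PFS or DOR analysis with these events counted, and the only efficacy sensitivity analysis in the available text concerns ORR (SAP 7.3.1).

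**Working it through.** **1. The rules side by side.**

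| Situation | Protocol 10.4.2 | SAP Table 2 |
|---|---|---|
| Alive, no progression | Censored at last evaluable assessment | Censored at last valid scan |
| Left the study | Censored at last assessment before leaving | Censored at last valid scan |
| New anti-lymphoma treatment | Censored at last assessment before it | Censored at last valid scan on or before it |
| No baseline or postbaseline assessment (PFS) | Censored, 1 day | Censored, Day 1 |
| Death or IRC progression, no gap | Event | Event |
| Death or IRC progression after two or more missed scans, still on study, no new treatment | Event | Censored at last valid scan before the gap |

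Only the last line differs. The protocol result there follows from its event definition, not from a sentence about missed scans.

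**2. A worked case.** Scans fall at Weeks 8, 16 and 24, then every 12 weeks to Week 96 (SAP 7.2). Take a valid scan at Week 16, Weeks 24 and 36 missed, and progression at Week 48. The protocol gives a PFS event at Week 48; the SAP censors at Week 16. If Week 16 was also the first response, DOR is censored at its start.

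**3. Direction.** Kaplan-Meier survival is the product of (1 − d/n) over event times. The SAP rule removes one from d at the affected event, which raises the curve. It also removes one from n between the last valid scan and that event, which lowers it. Example of the second effect: valid scan at Week 24, Weeks 36 and 48 missed, progression at Week 60. Under the protocol this participant is at risk and event-free at 12 months. Under the SAP they leave the risk set at Week 24, so another participant's event between then and 12 months contributes 1 − 1/(n − 1) instead of 1 − 1/n. The 12-month estimate falls.

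**4. Illustrative size.** The documents state no figure to reproduce.

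- From the documents: 40 participants (SAP 3.3), the scan schedule (SAP 7.2), at least 12 months of follow-up (SAP 7.3).
- Assumed: exponential PFS with median 9, 12, 18 or 24 months; 5%, 10% or 20% of participants with an event preceded by two missed scans; follow-up uniform over 12 to 24 months.
- Two variants: progression found at the first scan after the gap, and death after the gap. There were 3,000 datasets per scenario, each analysed under both rules.

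Results, SAP rule minus protocol rule, in datasets with at least one affected participant:

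| Quantity | Range over scenarios |
|---|---|
| Mean 6-month PFS | +0.3 to +1.2 points |
| Mean 12-month PFS | +1.0 to +3.4 points |
| Mean 18-month PFS | +1.4 to +5.0 points |
| Median PFS higher | 15% to 87% of datasets |
| Median PFS lower | at most 1.7% of datasets |
| 12-month PFS lower | 7% to 28% of datasets |

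In the progression variant, 0.5 to 4.5 participants per trial were affected on average. A separate deaths-only simulation, averaged over all trials, assumed median time to progression of 16 months, 10% to 30% who stop scanning but stay on study, and a death hazard of 1% to 2% per week. It gave +0.3 to +1.5 points at 12 months.

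**5. Against sampling error.** Taking 12-month PFS as 0.58, within the simulated values, the standard error is √(0.58 × 0.42 / 40) = 0.078 and the 95% half-width is 1.96 × 0.078 = 0.153. A shift of 1.0 to 3.4 points is about 7% to 22% of that half-width. DOR was not simulated. At the planning ORR of 62% it would rest on 0.62 × 40 ≈ 25 responders.

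**The case against.** The strongest reply is that the rule has a stated source and a rationale. SAP 7.4.3 says Table 2 is based on FDA guidance, and the protocol's handling is not free of bias either: progression found at Week 48 after a last valid scan at Week 16 is dated Week 48, although it may have occurred months earlier. This stands. Which rule should be the main analysis is a genuine trade-off. A source for a rule does not, however, declare a departure from the protocol.

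The affected group is also narrow. Participants who left the study or began new therapy are censored under both documents, and those who cannot be reached are deemed withdrawn (Protocol 7.3). What remains is someone still on study, without new therapy, with two missed scans and then a documented event. This stands too. A reader might infer that everyone who stops being scanned after toxicity or decline is lost as an event only because of the SAP; the documents do not support that.

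A reader might also infer that the rule always flatters the drug. The Week 24 to Week 60 case shows otherwise; favourable on average is all that can be said.

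Finally, a reader might see Table 2 as contradicting itself, because a death after a gap also fits the row for death before a first progressive assessment, which is an event. The rows can be read as a general rule followed by a specific exception. What is missing is a statement of precedence.

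**Conclusion.** The departure is real and undeclared, and no planned output would show PFS or DOR as Protocol 10.4.2 defines them. On average the SAP rule raises PFS and its median. The simulated sizes rest on assumed rates of missed scans and events. The documents give no such rates, so the true size is unknown. With 40 participants it is probably small against sampling error. The deaths-only simulation in particular uses a high hazard: 1% to 2% per week is about 41% to 65% a year, from 1 − exp(−0.52) and 1 − exp(−1.04).

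The stakes are limited. PFS and DOR are secondary and descriptive, with no formal tests (Protocol 10.3, SAP 3.2). ORR, the futility rule and OS are untouched. The point is worth correcting because the correction is cheap and restores the protocol-defined estimates, not because a material distortion has been shown.

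**What to change.** Reconcile the SAP with Protocol 10.4.2 in one of two ways:

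- Count a documented progression or death after missed scans as an event in the main IRC PFS and DOR analyses, subject to the protocol's own censoring grounds, and move the missed-assessment rule to a labelled sensitivity analysis.
- Keep the rule in the main analysis, declare it in SAP 11.1, and report IRC PFS and DOR both ways.

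In either case, state in Table 2 that the missed-assessment row, where applied, takes precedence over the general death rows.

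The cost is SAP wording and one extra analysis of each endpoint. The reported PFS and DOR may be slightly less favourable when these events are counted.
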